6.2 Missing Data

Patients with missing information on the demographics including age, gender, race will be excluded from the study.

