Primary Objective 2	
 • VHA (01APR2013-31MAR2018) • Pooled VHA and LCED (01APR2013-31MAR2018) • LCED (01APR2013-31MAR2018) 	U-500R syringe initiators U-500R Kwikpen initiators U-500R device switchers
Secondary Objective 2a	
 • VHA (01APR2013-31MAR2018) • Pooled VHA and LCED (01APR2013-31MAR2018) • LCED (01APR2013-31MAR2018) 	U-500R syringe initiators U-500R Kwikpen initiators U-500R device switchers
Secondary Objective 2b	
 • LCED (01APR2013-31MAR2018) 	U-500R syringe initiators U-500R Kwikpen initiators U-500R device switchers
Research Objective 3		
Primary Objective 3	
 • Truven MarketScan Claims Database (01JUL2013-30JUN2018) 	U-500R syringe initiators U-500R Kwikpen initiators

[2018-7241 Study Identifier] Observational Study Protocol

Figure 1 Study Design for U-500R Syringe Initiation (Index Event 1a)

[figure not shown]
[figure not shown]
[figure not shown]

Figure 2 Study Design for U-500R Kwikpen Initiation (Index Event 1b)

[2018-7241 Study Identifier] Observational Study Protocol**Figure 3 Study Design for U-500R Device Switch (Index Event 2)**

The figures above depict a schematic representation of the study design using the study periods for the Truven MarketScan claims database.

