5.4 Time Periods

The study period will range from 01APR2013-31MAR2018 for VHA and LCED; and 01JUL2013-30JUN2018 for Truven MarketScan claims. The identification period will be 01JAN2014-30JUN2017 for VHA and LCED; and 01APR2014-30SEP2017 for Truven MarketScan claims; the baseline and follow-up periods will be 9 months pre- and 9 months post-index date, respectively (Figures 1-3).

[2018-7241 Study Identifier] Observational Study Protocol**5.5 Variables/Measures**

Table 3 presents the study variables and operational definitions.

Table 3 Variables and Definitions

Variable	Source	Definition
Exposure		
Insulin use	Truven: Outpatient pharmacy claims table VHA: Pharmacy file	Index Event 1a : any insulin use other than U-500R in the pre-index and U-500R syringe use in the post-index period; Index Event 1b : any insulin use other than U-500R in the pre-index and U-500R Kwikpen use in the post-index period; and Index Event 2 : U-500R syringe use in the pre-index and U-500R Kwikpen use in the post-index period.
Baseline Characteristics*		
Age	Truven: Inpatient service table, outpatient service table, outpatient pharmacy claims table VHA: Enrollment file	Age will be retained in the dataset as a continuous variable for groups aged 18-25, 26-35, 36-45, 46-55, 56-64, and ≥ 65 years.
Sex	Truven: Inpatient service table, outpatient service table, outpatient pharmacy claims table VHA: Enrollment file	A flag will be created for male and female patients.
Race (only VHA)	VHA: Enrollment file	A flag will be created for White, Black, and other race patients.
U.S Region (only Truven)	Truven: Inpatient service table, outpatient service table, outpatient pharmacy claims table	A flag will be created for patients belonging to Northeast, Northcentral, South and West regions
Medicare eligibility (Only Truven)	From Truven	A flag will be created for patients who are enrolled in Truven Medicare
Body mass index (BMI)	VHA: Vital Status file	BMI on the index date will be calculated and reported as a continuous variable.
Quan-Charlson comorbidity index (CCI) Score ¹⁶	Truven: Inpatient service table, outpatient service table VHA: Inpatient and outpatient files	Quan-CCI score will be constructed using enhanced ICD-9/10-CM codes for 17 different comorbid conditions.

[2018-7241 Study Identifier] Observational Study Protocol

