6.4 Other Analyses**6.4.1 Outcomes Analyses**

All the analyses will be performed separately in VHA, linked Truven claims and EMR data, Truven claims database, and the pooled VHA and linked Truven claims and EMR data.

Pooling Multiple Databases

The VHA and linked Truven Claims with EMR databases will be pooled. To remove potential duplicate patient records from multiple data sources, probabilistic matching will be utilized. Potential duplicate patients across the databases will be identified by a STATinMED Research algorithm using age, sex, hospital admission date, hospital discharge date, and primary discharge diagnosis.^{23,24} Identified patients with the same information for the variables listed above will be assumed to be the potential duplicated patient and flagged in the pooled dataset. The rate of duplicate patients is expected to be low based on references and a previous study (<1%).²³ Duplicate patients can be potentially retained in the analytic file if the rate is low. After pooling, we will check if there are any potential duplicates across datasets. If the % will be small (<3%), we will not delete any duplicates because the impact to the final outcomes are considered minimal. If the % is significant (>3%), we will remove the duplicated records from the dataset that has the

[2018-7241 Study Identifier] Observational Study Protocol

larger sample size. Analyses will be conducted on each individual database as well as the pooled dataset.

Research Objective 1: Primary Objective 1Descriptive Analysis

All study variables including demographics, clinical characteristics, and treatment patterns of insulin (i.e., TDD, adherence, prescription fill rate, claim gaps, persistence, and concomitant medication use) will be analyzed descriptively before and after U-500R syringe initiation and U-500R Kwikpen initiation, and before and after U-500R device switch from syringe to Kwikpen.

Numbers and percentages will be provided for dichotomous and polychotomous variables. Means and standard deviations (SDs) will be provided for continuous variables. McNemar's test will be used to determine statistical significance of before and after values for categorical variables, and the paired t-test will be used to assess the statistical significance of before and after values in continuous variables.

Multivariate Analysis

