Mixed linear model will be used to evaluate factors associated with insulin adherence in the pre- and post-index periods among U-500R syringe initiators, U-500R Kwikpen initiators, and U-500R device switchers. Mixed linear model is used for studies with a longitudinal feature in which a continuous outcome variable is measured for the same subject repeatedly over the time period. Based on the distribution of the data, observations measured for the same subject are likely to be correlated over the study period and these data are considered as "multilevel" data. In addition, mixed linear model has a mixed effect consisting both fixed and random effects. Time-varying and time invariant variables such as demographic characteristics can be both included in the model. In the current model, adherence which is measured at two time intervals (before and after the index event; U-500R initiation/device switch), will be considered the dependent variable. Observed TDD will be considered as the time varying covariate (measured both before and after the index event) in the model, and the time independent covariates include the demographic and clinical characteristics.

The complete list of time varying and time-independent covariates will include:

- age
- sex
- race
- BMI
- baseline CCI score
- observed TDD from claims
- time (pre/post)

[2018-7241 Study Identifier] Observational Study Protocol

Note: Age, sex, race, BMI, and CCI score will be assessed during pre-index period. Adherence (PDC) and observed TDD will be calculated during the entire pre-index and post-index periods, respectively.

Research Objective 2: Primary Objective 2Descriptive Analysis

HbA1c will be analyzed descriptively before and after U-500R syringe initiation and U-500R Kwikpen initiation, and before and after U-500R device switch from syringe to Kwikpen.

Numbers and percentages will be provided for dichotomous and polychotomous variables. Means and standard deviations (SDs) will be provided for continuous variables. McNemar's test will be used to determine statistical significance of before and after values for categorical variables, and the paired t-test will be used to assess the statistical significance of before and after values in continuous variables.

Multivariate Analysis: HbA1c

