a longitudinal feature in which a continuous outcome variable is measured for the same subject repeatedly over the time period. Based on the distribution of the data, observations measured for the same subject are likely to be correlated over the study period and these data are considered as “multilevel” data. In addition, mixed linear model has a mixed effect consisting both fixed and random effects. For this objective, mixed linear model helps to evaluate the effect of both time varying and time-independent variables on the costs, while taking into account for correlation due to multiple assessments from the same individual. In the current model, costs which are measured at two time intervals (before and after the index event; U-500R initiation), will be considered the dependent variable. Observed TDD will be considered as the time varying covariates in the model (measured both before and after the index date), and the time-independent covariates will include the demographic and clinical characteristics.

The complete list of covariates will include:

- age
- sex
- region
- baseline CCI score
- observed TDD from claims
- Medicare (yes/no)
- time (pre/post)

Note: For all the multivariate analyses the covariates will be included as per the availability in each of the VHA, Truven claims, linked Truven claims and EMR data and pooled VHA and linked Truven data. Age, sex, region, medicare (yes/no), and CCI score will be assessed during pre-index period. Observed TDD will be calculated during the entire pre-index and post-index periods, respectively.

Adherence will not be included as one of the covariates here due to the high collinearity between time and adherence. Hence, further mediation analysis will be performed to determine the mediator effect of adherence on costs.

Mediation Analysis:

Mediation analysis following the Baron and Kenny’s steps will be considered to understand the impact of index event (time) on costs through potential mediators. Adherence is considered as a potential mediator between the costs and time. The key steps in mediation analysis include a model of the mediator (adherence) as a function of the predictor (time) and a model of the outcome (costs) as a function of both the mediator (adherence) and the predictor (time). Bootstrapping method will be used to test the effect of mediator. The detailed steps are described below:

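### The missing-data rule excludes patients without race from the whole study, although race is a VHA-only variable; read literally it removes every MarketScan patient, and perhaps every LCED patient

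*Protocol*

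**What the plan says.** Section 6.2 is a single sentence: "Patients with missing information on the demographics including age, gender, race will be excluded from the study". It acts on membership of the study, not on a particular model or database.

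Table 3 in Section 5.5 restricts race to VHA, gives the VHA enrollment file as its only source, and defines three levels: "A flag will be created for White, Black, and other race patients". There is no level for unknown or uncollected race.

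Table 1 in Section 5.1 assigns databases to objectives. Primary Objective 3 is run in MarketScan claims alone and Secondary Objective 2b in LCED alone. The other objectives use VHA, the pooled VHA and LCED data, and one further Truven source. Section 6.4.1 is broader still: "All the analyses will be performed separately in VHA, linked Truven claims and EMR data, Truven claims database, and the pooled VHA". The last item in that list is VHA pooled with LCED.

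The models for Primary Objectives 1 and 2 and Secondary Objective 2a list race as a covariate. The cost model for Primary Objective 3 does not; it lists region and Medicare status. A note after the cost model says, of the adjusted models only, that "the covariates will be included as per the availability in each of the VHA, Truven claims, linked Truven claims and EMR data". Its list of sources ends with the pooled set.

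On BMI, Table 3 says "BMI on the index date will be calculated and reported as a continuous variable", while the model notes in Section 6.4.1 say "Age, sex, race, BMI, and CCI score will be assessed during pre-index period".

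**The concern.** A rule that excludes for a missing value does harm when the value is never collected in some of the sources. MarketScan and LCED are in the study because VHA lacks certain outcomes, such as out-of-pocket costs, and to improve generalizability and sample size. An exclusion that only VHA patients can survive would defeat those purposes, and Primary Objective 3 cannot be answered anywhere but MarketScan.

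Two practical questions remain even if nobody would apply the rule literally. In the pooled models race is listed but may be absent for all LCED patients. The text does not say whether to drop those patients, drop race or add a level, and these choices give different populations or different models. In VHA, patients are removed from analyses in which race plays no part.

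**Working it through.** No sample-size or error-rate figure is at issue, so the check applies the Section 6.2 rule to each objective-by-database combination in Table 1, using the availability of race stated in Table 3.

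| Objective | VHA | Pooled VHA and LCED | LCED | MarketScan |
|---|---|---|---|---|
| Primary 1 | loses unknown race | VHA only* | not planned | empty |
| Primary 2 | loses unknown race | VHA only* | empty* | not planned |
| Secondary 2a | loses unknown race | VHA only* | empty* | not planned |
| Secondary 2b | not planned | not planned | empty* | not planned |
| Primary 3 | not planned | not planned | not planned | empty |

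*Conditional on the VHA-only label also covering the linked EMR.

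Count: 3 VHA + 3 pooled + 3 LCED + 2 MarketScan = 11 combinations.

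- Certainly emptied: 2 of 11 (both MarketScan).
- Conditionally emptied: 3 of 11 (LCED), for a total of 2 + 3 = 5 of 11.
- Conditionally reduced to VHA alone: 3 of 11 (pooled).
- Reduced by the number with unknown race: 3 of 11 (VHA).

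Next, whether any other text limits the rule:

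- The availability note ("the covariates will be included as per the availability in each of the VHA, Truven claims, linked Truven claims and EMR data") concerns which terms enter the multivariate models. It does not reach the descriptive cost comparisons, nor Secondary Objective 2b, for which Section 6.4.1 plans no multivariate analysis. It does not restore a patient who has already been excluded.
- The note closing Section 5.3.1 waives the HbA1c criterion for Truven claims because that source has no laboratory data. The protocol therefore writes an express waiver when a criterion cannot apply to a source; there is none for race.

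Within VHA, the unadjusted before/after comparisons are paired t-tests and McNemar's tests, each using only a patient's own pre- and post-index values. The loss is p × n, where p is the share with unknown race and n the cohort after selection. The protocol gives neither. The counts in Table 4 (for example 4,120 for Kwikpen) precede most of the Section 5.3.1 criteria and cannot stand for n.

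If the exclusion is limited to age and sex, absent race empties 0 of the 11 combinations.

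**The case against.** The strongest reply is that the literal reading proves too much. The list in Section 6.2 is open-ended, and Table 3 also has Truven-only variables, region and Medicare eligibility. If a field that a source never collects counted as missing, VHA patients could be excluded for having no region, and the whole study would be empty. The sensible reading is that a value is missing only where the source records that variable. The race-free cost model and the availability note support this. It stands as evidence of intent, but it does not mend the text: Section 6.2 names race and does not name region, and intent does not settle the pooled models, which list race.

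The LCED part is uncertain. Table 3's source column is visibly incomplete for the EMR: HbA1c lists only the VHA laboratory file although Primary Objective 2 uses LCED, and BMI lists only VHA although LCED is described as holding vitals. The label may contrast VHA with Truven claims only. This stands, and the LCED results are conditional for that reason.

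It can also be said that excluding VHA patients without race is an ordinary complete-case choice and that race is a factor of interest in the models. For the models this has force: with time-varying dose, or in the zero-inflated count model, a fixed covariate can shift the estimated time effect. A reader might infer that race is irrelevant to every before/after contrast, but that is exact only for the unadjusted paired tests.

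**Conclusion.** The point holds as a fault in a stated rule. Applied as written, Section 6.2 empties Primary Objective 3 and the MarketScan arm of Primary Objective 1. If race is also absent from the linked EMR, it empties Secondary Objective 2b and the LCED arms of Primary Objective 2 and Secondary Objective 2a, and reduces the pooled set to VHA. The MarketScan part rests only on Tables 1 and 3; the LCED part rests on how far the VHA-only label reaches.

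Two stronger readings are not supported. A reader might infer that the sponsor plans to discard all Truven patients; the cost model shows otherwise, so this is a rule to be corrected, not a plan to run empty analyses. A reader might also infer a particular loss in VHA; the protocol gives no rate of unknown race and no post-selection count, so the loss exists in principle but cannot be sized.

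The BMI wording is a separate and minor inconsistency. Section 6.2 does not name BMI, so it cannot be concluded that patients without a measurement on the index date would be dropped.

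**What to change.** Before the cohorts are built:

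1. Limit the Section 6.2 exclusion to missing age or sex.
2. In VHA, keep patients with unknown race in the unadjusted paired analyses and carry them in the models under an unknown level, added to the three levels in Table 3.
3. Omit race from models in any database that does not record it, and state whether LCED does.
4. In the pooled VHA and LCED models, use a data-source indicator so that LCED patients are not dropped for absent race. If LCED patients get a not-recorded race level of their own, that level coincides with the indicator, so only one of the two should be entered.
5. Separately, reconcile the two BMI definitions, the index date in Table 3 and the pre-index period in the model notes.

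The cost is a few sentences, with no new data, and no patient is lost. The small downside is that an unknown-race level adjusts more crudely than complete race data would.

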6.3 Significance Levels

Two-sided hypothesis testing will be applied to test the statistical significance, and multiple testing adjustment for controlling error rates will not be applied. A p-value of <0.05 will be considered statistically significant. SAS for Windows Version 9.4 will be used for all statistical analyses.

6.4 Other Analyses**6.4.1 Outcomes Analyses**

All the analyses will be performed separately in VHA, linked Truven claims and EMR data, Truven claims database, and the pooled VHA and linked Truven claims and EMR data.

Pooling Multiple Databases

The VHA and linked Truven Claims with EMR databases will be pooled. To remove potential duplicate patient records from multiple data sources, probabilistic matching will be utilized. Potential duplicate patients across the databases will be identified by a STATinMED Research algorithm using age, sex, hospital admission date, hospital discharge date, and primary discharge diagnosis.^{23,24} Identified patients with the same information for the variables listed above will be assumed to be the potential duplicated patient and flagged in the pooled dataset. The rate of duplicate patients is expected to be low based on references and a previous study (<1%).²³ Duplicate patients can be potentially retained in the analytic file if the rate is low. After pooling, we will check if there are any potential duplicates across datasets. If the % will be small (<3%), we will not delete any duplicates because the impact to the final outcomes are considered minimal. If the % is significant (>3%), we will remove the duplicated records from the dataset that has the

[2018-7241 Study Identifier] Observational Study Protocol

larger sample size. Analyses will be conducted on each individual database as well as the pooled dataset.

Research Objective 1: Primary Objective 1Descriptive Analysis

All study variables including demographics, clinical characteristics, and treatment patterns of insulin (i.e., TDD, adherence, prescription fill rate, claim gaps, persistence, and concomitant medication use) will be analyzed descriptively before and after U-500R syringe initiation and U-500R Kwikpen initiation, and before and after U-500R device switch from syringe to Kwikpen.

Numbers and percentages will be provided for dichotomous and polychotomous variables. Means and standard deviations (SDs) will be provided for continuous variables. McNemar's test will be used to determine statistical significance of before and after values for categorical variables, and the paired t-test will be used to assess the statistical significance of before and after values in continuous variables.

Multivariate Analysis

Mixed linear model will be used to evaluate factors associated with insulin adherence in the pre- and post-index periods among U-500R syringe initiators, U-500R Kwikpen initiators, and U-500R device switchers. Mixed linear model is used for studies with a longitudinal feature in which a continuous outcome variable is measured for the same subject repeatedly over the time period. Based on the distribution of the data, observations measured for the same subject are likely to be correlated over the study period and these data are considered as "multilevel" data. In addition, mixed linear model has a mixed effect consisting both fixed and random effects. Time-varying and time invariant variables such as demographic characteristics can be both included in the model. In the current model, adherence which is measured at two time intervals (before and after the index event; U-500R initiation/device switch), will be considered the dependent variable. Observed TDD will be considered as the time varying covariate (measured both before and after the index event) in the model, and the time independent covariates include the demographic and clinical characteristics.

The complete list of time varying and time-independent covariates will include:

- age
- sex
- race
- BMI
- baseline CCI score
- observed TDD from claims
- time (pre/post)

[2018-7241 Study Identifier] Observational Study Protocol

Note: Age, sex, race, BMI, and CCI score will be assessed during pre-index period. Adherence (PDC) and observed TDD will be calculated during the entire pre-index and post-index periods, respectively.

Research Objective 2: Primary Objective 2Descriptive Analysis

HbA1c will be analyzed descriptively before and after U-500R syringe initiation and U-500R Kwikpen initiation, and before and after U-500R device switch from syringe to Kwikpen.

Numbers and percentages will be provided for dichotomous and polychotomous variables. Means and standard deviations (SDs) will be provided for continuous variables. McNemar's test will be used to determine statistical significance of before and after values for categorical variables, and the paired t-test will be used to assess the statistical significance of before and after values in continuous variables.

Multivariate Analysis: HbA1c

Mixed linear model will be used to evaluate factors associated with HbA1c level in the pre- and post-index periods among U-500R syringe initiators, U-500R Kwikpen initiators, and U-500R device switchers. Mixed linear model is used for studies with a longitudinal feature in which a continuous outcome variable is measured for the same subject repeatedly over the time period. Based on the distribution of the data, observations measured for the same subject are likely to be correlated over the study period and these data are considered as "multilevel" data. In addition, mixed linear model has a mixed effect consisting both fixed and random effects. For this objective, mixed linear model helps to evaluate the effect of both time varying and time-independent variables on the HbA1c, while taking into account for correlation due to multiple assessments from the same individual. In the current model, HbA1c level which is measured at two time intervals (before and after the index event; U-500R initiation/device switch), will be considered the dependent variable. Observed TDD will be considered as the time varying covariate in the model (measured both before and after the index event), and the time independent covariates include the demographic and clinical characteristics.

The complete list of covariates will include:

- age
- sex
- race
- BMI
- baseline CCI score
- observed TDD from claims
- time (pre/post)

Note: Age, sex, race, BMI, and CCI score will be assessed during pre-index period. Observed TDD will be calculated during the entire pre-index and post-index periods, respectively. Pre-index

[2018-7241 Study Identifier] Observational Study Protocol

HbA1c will be defined as the HbA1c measurement -90/+30 days of the index date. For patients with multiple HbA1c measurements within this period, the measurement taken closest to the index event date will be reported as the pre-index HbA1c value. Post-index HbA1c will be defined as the HbA1c within 2 months of the end of the follow-up period.

Adherence will not be included as one of the covariates here due to the high collinearity between time and adherence. Hence, further mediation analysis will be performed to determine the mediator effect of adherence on HbA1c.

Mediation Analysis:

Mediation analysis following the Baron and Kenny's steps will be considered to understand the impact of index event (time: pre-index indicates use of othe insulin and post-index indicates U-500R use) on HbA1c through potential mediators. Adherence is considered as a potential mediator between the HbA1c and time. The key steps in mediation analysis include a model of the mediator (adherence) as a function of the predictor (time) and a model of the outcome (HbA1c) as a function of both the mediator (adherence) and the predictor (time). Bootstrapping method will be used to test the effect of mediator. The detailed steps are described below:

Step 1: Effect of predictor (time) on the outcome (HbA1c):

In the first step, the effect of time on the dependent variable HbA1c will be assessed. Statistically, a significant relationship between the two variables will trigger the next step of the mediation analysis. However, it is suggested that the clinical significance and theoretical evidence should be considered in the case of failure to detect an association that is statistically significant. Since the effect of time on HbA1c is the primary interest of this analysis, we will carry out the next step regardless of the significance between time and HbA1c.

Step 2: Effect of predictor (time) on the mediator (adherence):

The effect of time (predictor) on the hypothesized mediator adherence will be assessed, and adherence will be considered as a dependent variable in the model. Potential mediation effect will be supported by a statistically significant relationship between time and adherence, which will lead to the next step of the analysis.

Step 3: Combined effect of predictor (time) and mediator (adherence) on the outcome (HbA1c):

Adherence will be included and adjusted as a covariate in the model assessing the relationship between time (predictor) and the dependent variable HbA1c. Evidence of a mediation effect will be strengthened if the relationship between time and HbA1c disappears or weakens while adjusting for adherence. If the effect of time on HbA1c became insignificant, this indicates that the relationship between time and HbA1c is fully mediated by adherence (full mediation); and if the relationship remains significant with a reduced magnitude, this indicates that adherence is partially meditating the relationship between time and HbA1c (partial mediation). If any of the mediation effect exists, the next step will be used to further test the significance of the mediation effect.

[2018-7241 Study Identifier] Observational Study Protocol

Step 4: Assess the statistical significance of the effect of the mediator (adherence):

Bootstrapping method will be applied to evaluate the statistical significance of the adherence. At least 500 bootstrapping sample will be applied. All estimates will be combined in one dataset to compute the indirect, direct and total effects. The summary of effects table along with the bootstrap estimates and p-values will be provided. If the p-value of the indirect effect is significant, this clearly indicates that the mediation effect is significant. Additionally, the direct effect of time on the outcome HbA1c, as well as the total effect, which is a sum of the indirect and direct effect and the percentage mediated will be provided.

Research Objective 2: Secondary Objective 2aDescriptive Analysis

Number of hypoglycemia events will be analyzed descriptively before and after U-500R syringe initiation and U-500R Kwikpen initiation, and before and after U-500R device switch from syringe to Kwikpen.

Numbers and percentages will be provided for dichotomous and polychotomous variables. Means and standard deviations (SDs) will be provided for continuous variables. McNemar's test will be used to determine statistical significance of before and after values for categorical variables, and the paired t-test will be used to assess the statistical significance of before and after values in continuous variables.

Multivariate Analysis: Hypoglycemia Event

Zero-inflated negative binomial mixed model will be used to evaluate factors associated with number of hypoglycemia events PPPY in the pre- and post-index periods among U-500R syringe initiators, U-500R Kwikpen initiators, and U-500R device switchers. Zero-inflated negative binomial distribution is a mixture of a binary distribution that is degenerate at zero and an ordinary count distribution such as negative binomial. In cases of outcome variable being repeatedly measured from the individual subjects, zero inflated models are extended to include random effects to account for the correlation among the repeated measures within a subject. In the current model, the number of hypoglycemia events which might have more zeroes (for example not every patient might have a lab visit for glucose) and is measured at two time intervals (before and after the index event; U-500R initiation/device switch), will be considered the dependent variable. Observed TDD, and HbA1c will be considered as the time varying covariates in the model (measured both in the before and after index date), and the time-independent covariates will include the demographic and clinical characteristics.

The complete list of covariates will include:

- age
- sex
- race
- BMI
- baseline CCI score

[2018-7241 Study Identifier] Observational Study Protocol

- observed TDD from claims
- HbA1c
- time (pre/post)

Note: Age, sex, race, BMI, and CCI score will be assessed during pre-index period. Observed TDD and HbA1c will be calculated during the entire pre-index and post-index periods, respectively. Pre-index HbA1c will be defined as the HbA1c measurement -90/+30 days of the index date. For patients with multiple HbA1c measurements within this period, the measurement taken closest to the index event date will be reported as the pre-index HbA1c value. Post-index HbA1c will be defined as the HbA1c within 2 months of the end of the follow-up period.

Research Objective 2: Secondary Objective 2bDescriptive Analysis

Treatment outcomes (HbA1c and number of hypoglycemic events) and prescriber behavior (observed TDD in claims and prescribed TDD from the physician) will be analyzed descriptively and quarterly before and after U-500R syringe initiation and U-500R Kwikpen initiation, and before and after U-500R device switch from syringe to Kwikpen.

Numbers and percentages will be provided for dichotomous and polychotomous variables. Means and standard deviations (SDs) will be provided for continuous variables. McNemar's test will be used to determine statistical significance of before and after values for categorical variables, and the paired t-test will be used to assess the statistical significance of before and after values in continuous variables.

Multivariate Analysis

No multivariate analysis will be applied for Secondary Objective 2b.

Research Objective 3: Primary Objective 3Descriptive Analysis

Health care total costs and out-of-pocket costs will be analyzed descriptively before and after U-500R syringe initiation and U-500R Kwikpen initiation. More specifically, among the U-500R initiators, all the variables will be compared before and after U-500R syringe initiators and U-500R Kwikpen initiators.

Numbers and percentages will be provided for dichotomous and polychotomous variables. Means and standard deviations (SDs), along with the median, minimum and maximum will be provided for continuous variables. McNemar's test will be used to determine statistical significance of before and after values for categorical variables, and the paired t-test will be used to assess the statistical significance of before and after values in continuous variables.

Multivariate Analysis

Generalized linear mixed model with log link will be used to evaluate factors associated with total health care costs and out-of-pocket costs in the pre- and post-index periods among U-500R syringe initiators and U-500R Kwikpen initiators. Generalized linear mixed model is used for studies with

[2018-7241 Study Identifier] Observational Study Protocol

a longitudinal feature in which a continuous outcome variable is measured for the same subject repeatedly over the time period. Based on the distribution of the data, observations measured for the same subject are likely to be correlated over the study period and these data are considered as “multilevel” data. In addition, mixed linear model has a mixed effect consisting both fixed and random effects. For this objective, mixed linear model helps to evaluate the effect of both time varying and time-independent variables on the costs, while taking into account for correlation due to multiple assessments from the same individual. In the current model, costs which are measured at two time intervals (before and after the index event; U-500R initiation), will be considered the dependent variable. Observed TDD will be considered as the time varying covariates in the model (measured both before and after the index date), and the time-independent covariates will include the demographic and clinical characteristics.

The complete list of covariates will include:

- age
- sex
- region
- baseline CCI score
- observed TDD from claims
- Medicare (yes/no)
- time (pre/post)

Note: For all the multivariate analyses the covariates will be included as per the availability in each of the VHA, Truven claims, linked Truven claims and EMR data and pooled VHA and linked Truven data. Age, sex, region, medicare (yes/no), and CCI score will be assessed during pre-index period. Observed TDD will be calculated during the entire pre-index and post-index periods, respectively.

Adherence will not be included as one of the covariates here due to the high collinearity between time and adherence. Hence, further mediation analysis will be performed to determine the mediator effect of adherence on costs.

Mediation Analysis:

Mediation analysis following the Baron and Kenny’s steps will be considered to understand the impact of index event (time) on costs through potential mediators. Adherence is considered as a potential mediator between the costs and time. The key steps in mediation analysis include a model of the mediator (adherence) as a function of the predictor (time) and a model of the outcome (costs) as a function of both the mediator (adherence) and the predictor (time). Bootstrapping method will be used to test the effect of mediator. The detailed steps are described below:

[2018-7241 Study Identifier] Observational Study Protocol*Step 1: Effect of predictor (time) on the outcome (costs):*

In the first, the effect of time on the dependent variable costs will be assessed. Statistically, a significant relationship between the two variables will trigger the next step of the mediation analysis. However, it is suggested that the clinical significance and theoretical evidence should be considered in the case of failure to detect an association that is statistically significant. Since the effect of time on costs is the primary interest of this analysis, we will carry out the next step regardless of the significance between time and costs.

Step 2: Effect of predictor (time) on the mediator (adherence):

The effect of time (predictor) on the hypothesized mediator adherence will be assessed, and adherence will be considered as a dependent variable in the model. Potential mediation effect will be supported by a statistically significant relationship between time and adherence, which will lead to the next step of the analysis.

Step 3: Combined effect of predictor (time) and mediator (adherence) on the outcome (costs):

Adherence will be included and adjusted as a covariate in the model assessing the relationship between time (predictor) and the dependent variable costs. Evidence of a mediation effect will be strengthened if the relationship between time and costs disappears or weakens while adjusting for adherence. If the effect of time on costs became insignificant, this indicates that the relationship between time and costs is fully mediated by adherence (full mediation); and if the relationship remains significant with a reduced magnitude, this indicates that adherence is partially mediating the relationship between time and costs (partial mediation). If any of the mediation effect exists, the next step will be used to further test the significance of the mediation effect.

Step 4: Assess the statistical significance of the effect of the mediator (adherence):

Bootstrapping method will be applied to evaluate the statistical significance of the adherence. The summary of effects table along with the bootstrap estimates and p-values will be provided. If the p-value of the indirect effect is significant, this clearly indicates that the mediation effect is significant. Additionally, the direct effect of time on the outcome costs, as well as the total effect, which is a sum of the indirect and direct effect and the percentage mediated will be provided.

7. Safety Evaluations

